#### 9.2. Serious Adverse Events

An AE is considered "serious" (SAE) if, in the view of either the investigator or Sponsor, it results in any of the following outcomes:

- Death
- A life-threatening AE

Note: An AE is considered "life-threatening" if, in the view of either the investigator or Sponsor, its occurrence places the patient or subject at immediate risk of death. It does not include an AE that, had it occurred in a more severe form, might have caused death.

• Inpatient hospitalization or prolongation of existing hospitalization

Note: The term "inpatient hospitalization" refers to any inpatient admission (even if less than 24 hours). For chronic or long-term inpatients, inpatient admission includes transfer within the hospital to an acute/intensive care inpatient unit. Inpatient hospitalization does not include: emergency room visits; outpatient/same-day/ambulatory procedures; observation/short stay units; rehabilitation facilities; hospice facilities; nursing homes; or clinical research/phase 1 units.

Note: The term "prolongation of existing hospitalization" refers to any extension of an inpatient hospitalization beyond the stay anticipated or required for the reason for the initial admission as determined by the investigator or treating physician.

• A persistent or significant incapacity or substantial disruption of the ability to conduct normal life functions

Note: An SAE specifically related to visual threat would be interpreted as any potential impairment or damage to the subject's eyes (e.g., hemorrhage, retinal detachment, central corneal ulcer or damage to the optic nerve).

- A congenital anomaly/birth defect in an offspring of a study subject.
- Other medically important event

Important medical events that may not result in death, are life-threatening, or require hospitalization may be considered serious when, based upon appropriate medical judgment, they may jeopardize the patient or subject and may require medical or surgical intervention to prevent one of the outcomes listed in this definition.

SAEs are collected at the time the subject signs the Informed Consent Form until the last follow up visit of the study.

#### 9.3. **Procedures for Reporting Adverse Events**

All AEs and their outcomes must be reported to the Sponsor and/or its designee, and the IRB/IEC as required by the IRB/IEC, federal, state, or local regulations and governing health authorities and recorded on the appropriate source documents.

#### 9.3.1. Reporting a Suspected Unexpected Adverse Reaction

All AEs that are 'suspected' and 'unexpected' are to be reported to the Sponsor and/or its designee and the IRB/IEC as required by the IRB/IEC, federal, state, or local regulations and governing health authorities.

#### 9.3.2. Reporting a Serious Adverse Event

To ensure subject safety, all SAEs, regardless of relationship to the study drug, must be immediately reported. All information relevant to the SAE must be recorded. The investigator is obligated to pursue and obtain information requested by the Sponsor and/or its designee. All subjects experiencing a SAE must be followed up and the outcome reported.

In the event of a SAE, the investigator must notify the Sponsor and/or it's designee immediately; obtain and maintain in his/her files all pertinent medical records, information, and medical judgments from colleagues who assisted in the treatment and follow-up of the subject; provide the Sponsor and/or its designee with a complete case history, which includes a statement as to whether the event was or was not suspected to be related to the use of the study drug; and inform the IRB of the SAE within their guidelines for reporting SAEs.

Refer to the SAE form for additional reporting instructions.

#### 9.4. Type and Duration of the Follow-up of Subjects after Adverse Events

The investigator will follow unresolved AEs to resolution until the subject is lost to follow- up or until the AE is otherwise classified. Resolution means the subject has returned to baseline state of health or the Investigator does not expect any further improvement or worsening of the AE. If the patient is lost to follow-up, the Investigator should make 3 reasonable attempts to contact the patient via telephone, post, or certified mail. All follow-up will be documented in the subject's source document.

If the Investigator becomes aware of any new information regarding an existing SAE (i.e., resolution, change in condition, or new treatment), a new SAE/Unanticipated Report Form must be completed and faxed to the Sponsor and/or its designee within 24 hours of the site's awareness of the new information. The original SAE form is not to be altered. The report should describe whether the event has resolved or continues and how the event was treated.

OPP-100 Protocol Amendment #2

#### **10. STATISTICAL ANALYSIS**

Statistical considerations and methods of analyses for this study are provided below; the accompanying Statistical Analysis Plan (SAP) contains complete details of the planned analyses.

#### **10.1.** Sample Size and Power Considerations

#### **10.2.** Analysis Populations

- Pharmacokinetics
- Safety Population

#### **10.3.** Statistical Hypotheses

No formal hypothesis will be tested.

#### **10.4.** Statistical Analysis

This section briefly outlines the planned analyses. The SAP describes the methods to be used in detail. If the SAP and the protocol disagree, the details and methods of the SAP will prevail.

#### **10.4.1.** General Considerations

# Outcome Action Image: Second second

CONFIDENTIAL

Page **30** of **44** 

#### 10.4.1.1. Subject Demographics and Baseline Characteristics

Continuous summary statistics will be generated for age in years by treatment group and for all subjects. Discrete summary statistics will be generated for the following qualitative demographic variables: age category, gender, ethnicity, race, and other baseline intranasal examination results, tabulated by treatment group and for all subjects. Individual subject data listings will support the Summary tables.

#### 10.4.2. Pharmacokinetic Analysis

10.4.2.1. Safety Analysis

CONFIDENTIAL

Page 31 of 44

#### 10.4.3. Interim Analysis

# 11. COMPLIANCE WITH GOOD CLINICAL PRACTICES, ETHICAL CONSIDERATIONS, AND ADMINISTRATIVE ISSUES

This study will be conducted in compliance with the protocol, Good Clinical Practices, including the International Conference on Harmonization (ICH) Guidelines, and in general, consistent with the Declaration of Helsinki. In addition, all applicable local, state, and federal requirements relevant to the use of study drugs in the countries involved will be adhered to.

#### **11.1. Protection of Human Subjects**

#### 11.1.1. Subject Informed Consent

The investigator or his/her representative will explain the nature of the study to the subject or his/her guardian or legal representative, and answer all questions regarding this study. Informed consent/assent must take place before any study specific procedures are initiated. Signed and dated written informed consent must be obtained from each subject and/or from the subject's parent or legal guardian prior to enrollment into the study. If the subject is under the legal age of consent, the consent form must be signed by a legal guardian or as required by state and/or local laws and regulations. A copy of the signed informed consent form will be given to the subject and the original will be placed in the subject's medical record.

All informed consent/assent forms must be approved for use by the Sponsor and receive approval/favorable opinion from an IRB prior to their use. If the consent form requires revision (e.g., due to a protocol amendment or significant new safety information), it is the investigator's responsibility to ensure that the amended informed consent is reviewed and approved by the Sponsor and/or it's designee prior to submission to the governing IRB and that it is read, signed and dated by all subjects subsequently enrolled in the study as well as those currently enrolled in the study.

If informed consent is taken under special circumstances (oral informed consent), then the procedures to be followed must be determined by the Sponsor and provided in writing by prior to the consent process.

OPP-100 Protocol Amendment #2

#### 11.1.2. Institutional Review Board Approval

This study is to be conducted in accordance with IRB regulations [U.S. 21 Code of Federal regulations (CFR) Part 56.103]. The investigator must obtain appropriate IRB approval before initiating the study and re-approval at least annually.

Only an IRB-approved version of the informed consent form will be used.

### **11.2.** Ethical Conduct of Study

This study will be conducted in accordance with the ethical principles that originated with the Declaration of Helsinki.

### **11.3.** Subject Confidentiality

All personal study subject data collected and processed for the purposes of this study should be maintained by the investigator and his/her staff with adequate precautions so to ensure the confidentiality of the data in accordance with local, state, and federal laws and regulations.

Monitors, auditors and other authorized representatives of the Sponsor, the IRB approving this study, the Food and Drug Administration, the Department of Health and Human Services, other domestic government agencies, and other foreign regulatory agencies will be granted direct access to the study subject's original medical and study records for verification of the data and/or clinical trial procedures. Access to this information will be permitted to the aforementioned individuals to the extent permitted by law.

A report of the results of this study may be published or sent to the appropriate health authorities in any country in which the study drug may ultimately be marketed, but the subject's identity will not be disclosed in these documents.

#### 11.4. Documentation

Source documents may include a subject's medical records, hospital charts, clinic charts, the investigator's study subject files, as well as the results of diagnostic tests such as X-rays, laboratory tests, and electrocardiograms. The investigator's copy of the CRFs serves as the investigator's record of a subject's study-related data.

#### 11.4.1. Retention of Documentation

All study related correspondence, subject records, consent forms, record of the distribution and use of all study drug and copies of CRFs should be maintained on file for at least two years after the last approval of a marketing application in an ICH region and until there are no pending or contemplated marketing applications in an ICH region; or until at least two years have elapsed since the formal discontinuation of clinical development of the study drug. These documents will

#### CONFIDENTIAL

Page **33** of **44** 

OPP-100 Protocol Amendment #2

be retained for a longer period if required by the applicable regulatory requirements or by an agreement with the Sponsor. It is the responsibility of the Sponsor to inform the investigator/institution as to when these documents no longer need to be retained.

If the responsible investigator retires, relocates, or for other reasons withdraws from the responsibility of keeping study records, custody must be transferred to a person who will accept the responsibility. The Sponsor must be notified in writing of the name and address of the new custodian.

# 11.5. Labeling, Packaging, Storage, Accountability, and Return or Disposal of Study Drug

#### 11.5.1. Labeling/Packaging

### 11.5.3. Accountability of Study Drug

OC-01/Chantix® must only be prescribed by the principal investigator or his/her named sub investigator(s) and is to only be used in accordance with this protocol. The study drugs must only be distributed to subjects properly qualified under this protocol to receive study drug. The investigator must keep an accurate accounting of the study drugs by maintaining a detailed inventory. This includes the amount of study drugs received by the site, amount dispensed to subjects, amount returned to the site by the subjects, and the amount returned to the Sponsor upon the completion of the study.

#### 11.5.4. Return or Disposal of Study Drug

OC-01 (varenicline) Nasal Spray will be returned to the Sponsor or their designee for destruction.

#### 11.6. Recording of Data

All subject data will be captured in the subject source documents. The investigator is responsible for ensuring that study data is completely and accurately recorded on each subject's source documents, and all study-related materials. All study data should also be attributable, legible, contemporaneous, and original

Data capture of all enrolled and randomized subjects will use software that conforms to 21 CFR Part 11 requirements, and will be performed only by staff who have been trained on the system and have access to the system. Data will not be analyzed for screen failure subjects. An audit trail will be maintained within the electronic system to capture all changes made within the database. After the end of the study and database lock, electronic copies of all applicable subjects' source documents will be provided to each Investigator Site to be maintained on file by the Investigator.

### 11.7. Handling of Biological Specimens

Blood samples (4 mL in K2EDTA tubes) are collected from an arm vein or catheter into Vacutainer tubes containing K2EDTA. Blood samples are mixed gently and maintained chilled until centrifuged within 2 hours of collection.

Plasma samples are separated into two equivalent aliquots and labeled appropriate with subject ID, site and nominal time point

All samples and associated results will be coded prior to being shipped from the site for analysis. Samples will be tracked using the unique identification number that is assigned to the subject.

#### **11.8.** Publications

The study will be documented in a final report, which will contain appropriate statistical analysis and medical overview. No individual site or Investigator may publish or present any results from the study until the Sponsor completes a joint publication of the trial in conjunction with various participating Investigators and appropriate sites contributing data and comments. Subsequently, individual Investigators may request to publish or present results from the trial; however, approval will be at the sole discretion of the Sponsor. Should the foregoing language be in conflict with the language addressing publication in the clinical trial agreement, the language in the Clinical Trial Agreement will prevail.

### **13. APPENDICES**

CONFIDENTIAL

Page **38** of **44** 

#### APPENDIX 1. SCHEDULE OF VISITS AND MEASUREMENTS

Procedure	Screening	Period 1 Check-In	Period 1	Period 2 Check-In	Period 2	End of Study/Early Termination
	Day -28 to -2	Day -1	Days 1-6	Day 14	Days 15-20	Day 27 + 7 Days
Informed consent/HIPAA	X			2		
Demographics	Х			2		
Medical history	X					
Eligibility criteria	X					
Urine pregnancy test 	Х					Х
Serum pregnancy test 		Х		х		
Drug and Alcohol Screen	Х	X		х		
Physical Examination 	X					Х
12-lead ECG	Х					Х
Vital Signs 	X		Х		Х	X
Laboratory Samples (hematology, chemistry) 	х		$X^4$		X 	x
Urinalysis	X					X
Intranasal Examination	Х	Х		X		Х
PK Sample Collection 			Х		Х	
Randomization			Х			
Administer OC-01 (varenicline) Nasal Spray/Chantix®			Х		х	
Concomitant medications	X	Х	Х	X	X	X
AE Query	5		Х	X	X	X

 For females of childbearing potential

Weight and height collected at Screening Visit only

Vital signs including heart rate, respiratory rate and blood pressure will be obtained at Screening, prior to treatment administration at Periods 1 and 2, and 2 hours post treatment administration at Periods 1 and 2, and End of Study/Early Termination.

Clinical Chemistry to be performed at Screening, and 2 hours post treatment administration Periods 1 and 2, and End of Study/Early Termination. Hematology to be performed at Screening and End of Study/Early Termination.

PK samples collected at the following timepoints post treatment administration (predose, 5 minutes, 15 minutes, 30 minutes, 1 hour, 2 hours, 3 hours, 4 hours, 6 hours, 6 hours, 8 hours, 12 hours, 24 hours, 36 hours, 48 hours, 72 hours, 96 hours, 120 hours). Samples collected up to and including 48 hours will be performed In-Unit. Following the 48 hour sample collection subjects will be discharged and return for remaining samples on an Out-Patient basis.

#### APPENDIX 2. EXAMINATION PROCEDURES, TESTS, EQUIPMENT, AND TECHNIQUES

The following examination procedures, tests, equipment and techniques are listed in this Appendix:

#### A1. Intranasal Examination

Qualified participants for the study must undergo an intranasal exam to make the final eligibility determination (e.g. severe nasal airway obstruction such as, severe septal deviation or inferior turbinate hypertrophy, or vascularized polyp seen on examination are reasons for exclusion). To monitor nasal mucosal integrity during the study for participant safety, an examination of the nasal cavities via an intranasal exam will be performed at the Screening Visit (after all other screening procedures have been completed), Periods 1 and 2 Check-in, and at the End of Study/Early Termination Visit. This examination will be performed by an Ear Nose and Throat (ENT) specialist, otolaryngologist or other suitably qualified medical practitioner (i.e. one who has been trained to perform intranasal exam). The procedure used for the intranasal exam can be conducted either by endoscopic examination or nasal specula.

#### A2. Laboratory Samples

The Schedule of Visits and Measurements (Appendix 1) defines the timepoints when each analyte should be collected. Table 2 below outlines the specific analytes to be tested:

#### Table 2:Laboratory Analytes

#### A3. Physical Examination

A physical examination will be conducted as per Standard of Care (SOC). Breast, genital and rectal examinations are not required unless specific evaluation is warranted. Physical examination findings should be recorded on the appropriate source document (e.g., medical history). Body

OPP-100 Protocol Amendment #2

height and weight will be collected at screening. Height should be measured in centimeters (without shoes). Weight should be measured in kilograms (without shoes).

#### A4. Vital Signs

Vital signs, including heart rate, respiratory rate and blood pressure will be obtained. Subjects must be in supine or sitting position in a rested and calm state for at least 5 minutes before blood pressure assessments are conducted. If the subject is unable to be in the supine position, the subject should be in the most recumbent position possible. The position selected for a subject should be the same that is used throughout the study. Vital sign assessments should be performed prior to blood sample collection.

#### A5. Electrocardiogram

A 12-lead ECG will be obtained during Screening and End of Study/Early Termination. Subject must be in a supine position in a rested and calm state for at least 5 minutes before ECG assessment is conducted. If the subject is unable to be in the supine position, the subject should be in the most recumbent position as possible.

The principal investigator or designated site physician will review all ECGs. Once signed, the original ECG tracing will be retained with the subject's source documents. ECG should be performed prior to blood sample collection.

APPENDIX 5.

CONFIDENTIAL

Page 44 of 44

behavior or thinking that are not typical for the patient are observed, or if the patient develops st	uicidal ideation or suicidal behavior. The healthcare provider should

### List of Abbreviations and Definitions

AE	adverse event
ANOVA	analysis of variance
ATC	Anatomical Therapeutic Chemical
AUC	area under the curve
AUC 0-t	area under the concentration-time curve from 0 to the last measurable concentration
AUC 0-∞	area under the concentration-time curve from 0 to infinity
BLQ	below limit of quantification
BMI	body mass index
CI	confidence interval
C max	maximum plasma concentration observed
CV	coefficient of variation
ECG	electrocardiogram
GM	geometric mean
Kel	elimination rate constant
LLOQ	lower Limit of Quantification
MedDRA	MedDRA
mg	milligrams
mL	milliliter
NCA	non-compartmental analysis
PK	pharmacokinetic
PT	preferred term
SAEs	serious adverse events
SAP	statistical analysis plan
SD	standard deviation
SOC	system organ class
T ½	terminal half-life
TEAEs	treatment-emergent adverse events
T max	time to reach the maximum concentration observed

WHO	World Health Organization
$\mu\text{L}$	microliter

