	5. If a female of childbearing potential who is not using an acceptable means of birth control (acceptable methods of contraception include: hormonal – oral, implantable, injectable, or transdermal contraceptives, mechanical – spermicide in conjunction with a barrier such as a diaphragm or condom, IUD, or surgical sterilization of partner), have a negative urine pregnancy test at the Screening Visit.
Exclusion Criteria:	Subjects must NOT:
	1. Have had nasal or sinus surgery (including history of application of nasal cautery) or significant trauma to these areas.
	2. Have a vascularized polyp, severely deviated septum, chronic recurrent nosebleeds, or severe nasal airway obstruction as confirmed by intranasal examination at the Screening Visit.
	5. Any contraindication to varenicline according to the applicable label.
	
 
Have severe renal impairment (estimated creatinine clearance less than 30mL per minute).
 

	
 
Have current concomitant use of snuff, chewing tobacco, e- cigarettes or cigarettes/cigars during the study.
 

	9
	10. Have any condition or history that, in the opinion of the investigator, may interfere with study compliance, outcome

Page 6 of 44

Evaluation Criteria						
Pharmacokinetic Endpoints:	Varenicline plasma AUC 0-<math>\infty</math> , AUC 0-t , C max , T max , T <math>\frac{1}{2}</math> , K el					
Safety Measures:	Adverse events, clinical chemistry, hematology and urinalysis, vital signs assessments, physical examinations, ECGs and intranasal examinations.					
Statistical Methods:	Pharmacokinetics					

Page 8 of 44

Page 9 of 44

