### 7. STUDY MATERIALS

#### 7.1. Drug Supply

• Treatment A: Single oral tablet of 1 mg varenicline (Chantix®)

Chantix® is supplied as 1 mg capsular biconvex, light blue film-coated tablet debossed with "*Pfizer*" on one side and "CHX 1.0" on the other side.

- Treatment B: OC-01 (varenicline) Nasal Spray delivered as a 50 µL spray (0.06 mg per each 50 µL spray) into each nostril for a total delivered dose of 0.12 mg.
  - OC-01 (varenicline) Nasal Spray will be formulated at the desired concentration in sodium phosphate buffers and sodium chloride as an aqueous solution and presented in an amber glass vial with a multi-use preservative-free nasal pump.
  - OC-01 (varenicline) Nasal Spray is preservative-free and intended for intranasal use only. The product should not be used if cloudy or if particulate matter are present.
  - OC-01 solution must be administered without dilution.

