#### **Out-Patient Blood PK Sampling**

Sample 15: 72 hours Sample 16: 96 hours

OPP-100 Protocol Amendment #2

Sample 17: 120 hours

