### 3.3 SAMPLE SIZE AND POWER CONSIDERATIONS

This study is designed to test the relative bioavailability of 2 treatments (single oral dose of 1 mg varenicline [Chantix®] and Intranasal dose of 0.12 mg varenicline [OC-01]).

[REDACTED]

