## 12. PHARMACOKINETIC ANALYSES

### 12.1 GENERAL CONSIDERATIONS

Pharmacokinetics parameters will be calculated by NCA (Non-compartmental analysis) and evaluated for the PK analysis set.

[REDACTED]

[REDACTED]

[REDACTED]

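### Does ending AUC0-t at each profile's last measurable concentration bias the nasal-to-oral comparison?

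*SAP*

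**What the plan says.** The SAP's List of Abbreviations and Definitions gives AUC0-t as "area under the concentration-time curve from 0 to the last measurable concentration". The Pharmacokinetic Endpoints row of the protocol synopsis, which opens with "Varenicline plasma AUC", names AUC0-∞ first, then AUC0-t, Cmax, Tmax, half-life and Kel.

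Treatment A is a 1 mg tablet. Treatment B is one spray "into each nostril for a total delivered dose of 0.12 mg" (protocol 7.1). Protocol 8.4 uses the same 17 sampling times in both periods, the last being "Sample 17: 120 hours".

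SAP 3.3 states: "This study is designed to test the relative bioavailability of 2 treatments". SAP 12.1 names non-compartmental analysis as the method. Protocol 3 and 10.3 say that no formal hypothesis is tested.

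The PK endpoint list (SAP 5.1), the rest of 12.1, and the bodies of 12.2 (primary analysis), 12.3 (concentrations), 12.4 (parameters) and 12.5 (missing values and outliers) are redacted. Protocol 6.1 and 10.4.2 show no content either. SAP 1 places the table and listing specifications in a separate document.

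**The concern.** AUC0-t has no fixed upper limit. When two treatments differ greatly in dose, the lower-dose profile tends to drop below the assay limit sooner, so its area covers a shorter window. Here the doses differ by 1/0.12 = 8.33. Dividing each area by its dose does not cure this, because it rescales the areas and leaves the windows unequal.

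The primary objective is relative bioavailability. If an AUC0-t ratio carried that comparison and nasal levels were lost before 120 h, the ratio would mix dose and assay sensitivity with bioavailability and understate the nasal route. An AUC cut at a time when both of a subject's profiles are measurable would need no new samples, so its absence from the visible text can look like an oversight.

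**Working it through.** The plan states no AUC ratio, so there is no figure to reproduce. The check asks how large the effect could be, whether the listed endpoints already deal with it, and whether the documents show that it arises.

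**Inputs from the documents.** Doses of 1 mg and 0.12 mg; 17 samples to 120 h in both periods; AUC0-t ending at the last measurable value; AUC0-∞ also an endpoint.

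**Assumptions, none of them in the documents.** One compartment; absorption rate ka = 1.2/h by both routes; equal bioavailability; half-life 12, 24 or 30 h; assay limit (LLOQ) 0.2%, 0.5%, 1% or 2% of oral Cmax; no noise.

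**Step 1: the shift in time.** With equal half-lives the nasal profile reaches a common limit log2(8.33) = 3.06 half-lives before the oral one.

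**Step 2: the last measurable sample, half-life 24 h.** The modelled nasal level at 120 h is 0.42% of oral Cmax. It doubles for each 24 h backwards: 0.84% at 96 h, 1.69% at 72 h, 3.37% at 48 h. The nasal profile is therefore last measurable at 120, 96, 72 and 48 h for limits of 0.2%, 0.5%, 1% and 2%. The oral level at 120 h is 0.42/0.12 = 3.5%, so the oral profile always reaches 120 h.

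**Step 3: the AUC0-t ratio.** The share of total area beyond time t is about f(t) = [ka/(ka − k)]·exp(−kt), with k = ln 2/24 = 0.0289/h and ka/(ka − k) = 1.0247. With t_n and t_o the last measurable nasal and oral times, the dose-normalised ratio relative to truth is [1 − f(t_n)]/[1 − f(t_o)].

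- f(120) = 1.0247 × 0.03125 = 0.032
- Limit 0.5%: f(96) = 0.064, so 0.936/0.968 = 0.97
- Limit 1%: f(72) = 0.128, so 0.872/0.968 = 0.90
- Limit 2%: f(48) = 0.256, so 0.744/0.968 = 0.77

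Full calculation on the 17 planned times (linear-up/log-down trapezoids, ka 1.2/h both routes):

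| Half-life | LLOQ 0.2% | 0.5% | 1% | 2% |
|---|---|---|---|---|
| 12 h | 0.99 | 0.95 | 0.88 | 0.79 |
| 24 h | 1.00 | 0.97 | 0.90 | 0.77 |
| 30 h | 1.00 | 1.00 | 0.95 | 0.86 |

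Slowing nasal absorption to 0.3/h gives the lowest equal-bioavailability value, 0.744 (24 h, 2%). A true raw ratio of 0.120 would then read 0.120 × 0.744 = 0.089. If nasal bioavailability is half of oral, the lowest value on the same grid is 0.475 (12 h, ka 0.6/h, 2%).

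**Step 4: the other listed AUC.** AUC0-∞ adds the last concentration divided by Kel to each area. Over the whole equal-bioavailability grid (nasal ka 1.2, 0.6 or 0.3/h) its ratio is 0.995 to 1.002 of truth. In the 24 h, 2% cell, where AUC0-t reads 0.77, AUC0-∞ reads 1.00.

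**Step 5: what the documents show.** For the concern to bite, an AUC0-t ratio must be reported and nasal levels must be lost early enough to matter. The first is decided in redacted text. The second depends on an assay limit and a half-life that are not visible. The abbreviation list includes ANOVA, CI, GM ("geometric mean"), BLQ and LLOQ ("lower Limit of Quantification"), and none of these appears elsewhere in the readable SAP. That suggests, without proving it, that a ratio analysis and a rule for values below the limit sit behind the redactions.

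**The case for a change.** The strongest case on the other side is that the dose gap is built into the design, so unequal windows are foreseeable. When nasal levels drop out before 120 h, the AUC0-t ratio was below truth in every equal-absorption case run. AUC0-t is a listed endpoint that readers will compare. AUC0-∞ is also not a perfect safeguard, because it relies more on the estimated Kel as the nasal tail is lost. The extrapolated nasal share is about 13% at 24 h with a 1% limit and 26% with a 2% limit. In noise-free runs at half bioavailability AUC0-∞ drifts up to 1.060. In one extreme simulated cell with noise (12 h, ka 0.3/h, half bioavailability, 2% limit) it could not be estimated in 57% of subjects and read 1.28 in the rest. A common-window AUC and a column showing last measurable time would cost little.

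The mechanism, its direction and this arithmetic stand. They do not add up to a fault in the plan. The extreme cell stacks four unfavourable assumptions, and the common-window AUC itself reads 0.89 there, so it is no clean remedy. With noise but equal bioavailability and ka 1.2/h, AUC0-∞ was 1.000 to 1.017 in all 12 cells. The extra outputs are a reasonable preference. They may already be in the redacted sections or the separate table specifications, and content hidden by redaction cannot be counted as missing.

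**Conclusion.** The concern does not hold. It rests on a standard definition in an abbreviation list, which sets no rule for how the treatments are compared. The visible plan already lists AUC0-∞, takes samples to 120 h in both periods, and tests no hypothesis that a low AUC0-t ratio could overturn.

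The possible effect on an AUC0-t ratio runs from nil to a reading of 0.74 of truth under equal bioavailability, and to 0.475 if nasal bioavailability is half of oral. Where it falls depends on assumed values for assay limit, half-life and absorption. It is essentially zero if nasal levels stay measurable to 120 h. At equal bioavailability and ka 1.2/h that needs a limit at or below 0.014%, 0.42% or 0.83% of oral Cmax for half-lives of 12, 24 or 30 h. This is sufficient for no bias but stricter than negligible bias requires: at 12 h a limit of 0.2% already gives 0.99.

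The conclusion rests on AUC0-∞ being available as listed, and on not reading redacted text as absent. If the full SAP made AUC0-t the sole basis of the comparison, with an assay limit high enough to truncate the nasal profiles, the question would be worth reopening.
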